12.3 Laboratory Certification and Reference Ranges

Before the initiation of this trial, the Principal Investigator, or nominee, will provide Faraday Pharmaceuticals, Inc. with a copy of the certification form, with certification number and expiration date for the clinical laboratories used in the trial. Reference ranges for each laboratory test used in this trial will be obtained from the relevant laboratory performing trial tests. In the event the clinical laboratories are changed during the trial, Faraday Pharmaceuticals, Inc. will be

promptly notified of the reason and date of the change and appropriate documentation will be submitted to verify the certification of the new laboratory.

All clinical laboratory tests will be conducted at the investigational site's local laboratory. All accreditation certificates and laboratory reference ranges will be obtained prior to the commencement of the trial at the investigational site.

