5.2 Number of Centers/Subjects

This study will be conducted at up to 20 centers in the USA and Europe. European sites are not using this version of the protocol and will not be submitted to the IND. Up to 160 STEMI patients are planned for enrolment in this study to obtain a final sample size of 80 patients.

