12.2.4 Troponin Levels

In order to calculate AUC 0-48 hours, serum troponin T levels will be measured at the following time points:

- Pre-study-drug
- 12, 24, 48 hours post-study drug

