14.1.4 Sample Size Estimation

Little data exists on the incidence of arrhythmias that occur over an extended period of time following AMI and monitoring strategies for this type of assessment have not been optimized in a clinical trial setting. The primary goal of our study is to characterize the occurrence of arrhythmias in this patient population for 14 days post-AMI and to determine the feasibility of using ambulatory patch ECG monitors to capture this data. These data should be regarded as exploratory with the objective of identifying a meaningful clinical end point that can be easily measured in future, pivotal studies that are adequately powered to detect differences across treatment groups.

Estimating a drop-out rate of approximately 50%, we will need to enroll up to 160 patients in order to obtain a final total sample size of 80 patients. A final sample size of 80 patients will provide 80% power to detect a 37% reduction in INF/VV assuming an SD of 10%, a 24% increase in MSI assuming an SD of 20% and a 39% reduction in Troponin AUC with an SD of 60%. Equal variance was assumed among groups with an unbalanced allocation of patients to placebo (n=20) and combined FDY-5301 treatment groups (n=60).

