11.4.2.5 Serum Levels of Troponin

The troponin AUC₀₋₄₈ will be derived from the serum levels of troponin collected at the following timepoints: Predose, 4, 12, 24 and 48 hours post-study drug. AUC₀₋₄₈ will be calculated using the linear trapezoidal method. Where possible, the derivation will be carried out using actual post-dose times recorded. If actual times are missing, nominal times may be used with sponsor approval.

Summary statistics (also including geometric means and geometric coefficient of variation [CV] %) for the serum levels will be produced by each treatment group and the combined FDY-5301 group for the derived AUC₀₋₄₈. The summary statistics for troponin AUC₀₋₄₈ will be presented in a similar way.

The derived AUC₀₋₄₈ will be logarithmically transformed, and an unpaired Student's T-test will be used analyze its differences between all three FDY-5301 groups (overall) and placebo.

The logarithmically transformed AUC₀₋₄₈ from each group will then be tested using a one-way ANOVA to obtain a common variance followed by a Dunnett's post-test to separately compare each FDY-5301 dose group to placebo.

The arithmetic least squares means of the treatment differences will be back-transformed to provide the geometric means and its 95% confidence interval.

The same summarization and statistical analyses will be repeated by baseline TIMI flow (grade 1 and lower, or, grade 2 and 3) and infarct type (anterior or other).

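### No common troponin T assay is set and the log AUC0-48 analysis has no assay term, so any difference between local assays costs precision in a powered outcome

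*Protocol*

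**What the plan says.** **Measurement.** Protocol 12.2.4 introduces the sampling schedule with "In order to calculate AUC 0-48 hours, serum troponin T levels will be measured at the following time points". It names the analyte but no assay, platform, unit or laboratory. The subsection sits under General Safety (12.2), in a section whose title names troponin. Protocol 12.3, in that same section, says "All clinical laboratory tests will be conducted at the investigational" site's local laboratory. Reference ranges come from the laboratory that performs the test. A laboratory may change mid-trial, subject to notification and certification documents.

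**Contrast.** Protocol 10 sends CMR to a central core laboratory, and Protocol 11 provides central, blinded reading of the wearable ECG. No such arrangement is stated for troponin.

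**Sites and randomization.** Protocol 5.2 says "This study will be conducted at up to 20 centers in the USA and Europe", and its next sentence says that European sites follow a different protocol version. Protocol 5.4 and 7.3 describe a computer-generated code and mention no stratification by site.

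**Power.** Protocol 14.1.4 says "A final sample size of 80 patients will provide 80% power" for three outcomes, including a "39% reduction in Troponin AUC with an SD of 60"%. It assumes an "unbalanced allocation of patients to placebo (n=20) and combined FDY-5301 treatment groups (n=60").

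**Analysis.** Under SAP 11.4.2.5 the AUC0-48 "will be logarithmically transformed, and an unpaired" t-test compares combined FDY-5301 with placebo. A one-way ANOVA with Dunnett comparisons follows for each dose. The analysis is repeated by TIMI flow and infarct type, but not by site or assay.

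**The concern.** The AUC is linear in the concentrations. If one assay reads a constant factor r above another, every AUC from it is multiplied by r, and its log AUC is shifted by ln r. Local reference ranges can flag an abnormal safety value, but SAP 11.4.2.5 does not use them, so nothing puts the AUCs on one scale. With treatment alone in the model, the shift goes into the residual variance. Of the three outcomes with a stated power, two come from centrally read CMR. Troponin AUC is the third, and the only one without a stated common measurement. At stake is the chance of detecting a real troponin effect, and the width of its confidence interval.

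**Working it through.** **1. The plan's own figure.** Inputs from Protocol 14.1.4: difference 39, SD 60 (both read as % of the placebo mean), n = 20 and 60. The noncentrality is 39 / (60 × √(1/20 + 1/60)) = 39 / (60 × 0.2582) = 2.52. On 78 df, power is 80.3% at one-sided 5% and 70.1% at two-sided 5% (normal approximation: 80.9% and 71.1%). The stated 80% therefore reproduces on the untransformed scale at one-sided 5%. The power statement gives neither alpha nor sidedness.

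**2. The scale that the SAP analyzes.** Reading 60% as a coefficient of variation, log SD = √ln(1 + 0.6²) = √0.3075 = 0.555. The effect is −ln(1 − 0.39) = 0.494. The noncentrality is 0.494 / (0.5545 × 0.2582) = 3.45, which gives 92.6% power at two-sided 5%. The 95% confidence interval planned in SAP 11.4.2.5 implies the two-sided level.

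**3. Adding an assay difference (assumed).** For two assays with shares p and 1 − p, the added log variance is p(1 − p)(ln r)². It is largest at 50:50, where it equals (ln r)²/4. Total log SD = √(0.3075 + (ln r)²/4).

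| r | added variance | log SD | power |
|---|---|---|---|
| 1 | 0 | 0.555 | 92.6% |
| 1.25 | 0.012 | 0.566 | 91.7% |
| 1.5 | 0.041 | 0.590 | 89.3% |
| 2 | 0.120 | 0.654 | 82.4% |
| 3 | 0.302 | 0.781 | 67.8% |

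On these assumptions power falls below 80% at about r = 2.2.

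**4. A second model, by simulation.** Here 20 equal sites have normally distributed site shifts on the log scale, with unstratified 20:60 allocation and 4,000 runs. Two-sided power of the plain t-test was 92%, 90%, 85% and 73% for a site SD of 0, 0.2, 0.3 and 0.5. Simulated type I error stayed near 5% (4.3% to 6.2% over all null cases).

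**5. Which adjustment.** In the same simulation, a model with 20 fixed site effects had about 83–84% two-sided power whatever the site SD. It was therefore worse than the plain t-test unless the spread was large (84% against 85% at 0.3, 84% against 73% at 0.5). One term for two assays costs far less: when the assays agree, power goes from 92.6% to about 92.3%. When they differ proportionally, the term removes the added variance in step 3.

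**The case against.** Five points on the other side carry weight.

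- **Local testing is inferred.** No sentence says that troponin T is run locally. SAP 11.5.2 limits clinical laboratory parameters to chemistry and hematology, Table 2 lists troponin apart from the safety laboratory tests, and Protocol 15.1 mentions central laboratory samples as a generic example. This stands as a caveat. Even so, 12.3 makes no exception and no other text assigns troponin elsewhere, so the text needs correcting whichever was intended.
- **The site count is unclear.** A reader might infer that 12.3 governs 20 centers in two regions. It does not show this, because European sites use a different version. This stands.
- **The loss may be small or already counted.** The documents give no r. Up to r = 1.25 the loss is about one point, and even at r = 2 power stays above 80% on the log scale. The source of the 60% is not given, so it may already contain assay spread. A reader might infer that the true SD must exceed 60%; the documents do not support that.
- **No bias.** A reader might also infer that a chance imbalance of assays between arms distorts the treatment ratio beyond the loss of power. It is the same variance, and the t-test's standard error already carries it.
- **The outcome is exploratory.** Protocol 14.1.3 and 14.1.6 class troponin AUC as secondary and exploratory, which limits the weight of the point. But the plan states a power for it, and the remedy is very cheap.

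**Conclusion.** The concern holds as a conditional loss of precision. As written, 12.3 sends troponin T to local laboratories with no common assay, and the SAP model cannot absorb a difference between them. The loss runs from zero if the assays agree, through about 3 points at r = 1.5 and 10 at r = 2, to about 25 at r = 3. These sizes assume that the 60% is a coefficient of variation without assay spread, a 50:50 mix of two assays, a purely proportional difference, 20 versus 60 patients and a two-sided 5% test. The documents support neither a claim of bias or type I error inflation nor a claim that the stated power is missed. The change is worth making because assay identity is recorded most reliably during the trial and the adjustment costs almost nothing.

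**What to change.** 1. In Protocol 12.3, state which laboratory measures troponin T and with which assay. Confirm the arrangement at European sites.
2. Record the troponin T assay and unit for each site, with the date of any mid-trial change.
3. In SAP 11.4.2.5, replace the t-test and one-way ANOVA on log AUC0-48 with a linear model containing treatment and assay type. Take the combined contrast and the Dunnett comparisons from that model. Use a few assay levels, not up to 20 fixed site effects.

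The cost is one CRF field and one or a few degrees of freedom: about 0.3 points of power with two assays that agree. The term removes proportional differences; offsets or unlike reporting limits would be only partly removed.

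Measuring all troponin T in one laboratory would be cleaner, but the documents do not show that it is feasible on samples already drawn. Biomarker samples are serum in Protocol 12.2.5 and plasma in SAP 11.4.2.6, and residual volume is not documented. The SAP's troponin AUC also uses a 4-hour sample that Protocol 12.2.4 does not list. Those passages must be reconciled, and matrix, volume and time points confirmed, before that option is considered.

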13 SAFETY: ADVERSE EVENTS

13.1 Definitions

An **Adverse Event (AE)** is defined as any untoward medical occurrence in a subject, or clinical investigation subject administered an investigational product (pharmaceutical) and which does not necessarily have a causal relationship with this treatment. An AE can therefore be any unfavorable and unintended sign (including an abnormal laboratory finding), symptom, or disease temporarily associated with the use of a medicinal (investigational) product, whether or not related to the investigational product. A relationship to the investigational product is not necessarily proven or implied.

All adverse events occurring after a dose of investigational product observed by the investigator or reported by the subject (whether or not attributed to investigational product), will be reported on the case report form.

Given that this study specifically recruits STEMI patients, the MI itself will not be characterized as an AE.

However, complications arising as a consequence of the MI, for example emergent or worsening heart failure, death, or known arrhythmias will be specifically documented as adverse events in the CRFs.

Adverse events will be followed until resolved or considered stable out to 3 months. The only serious adverse event that will be tracked longer than 3 months is the incidence of death. All-cause mortality and cardiac-related mortality will be documented by phone call to the patient at 6 months. If the patient is unavailable, then mortality status will be obtained through physician/investigator records. The following attributes must be assigned by the investigator: description; dates of onset and resolution; severity; assessment of relatedness to investigational product, other suspect drugs, and action taken. The investigator may be asked to provide follow-up information.

13.2 Relationship to Study Drug

The principal investigator (PI) will classify every AE according to its relationship to study drug or trial-related procedures. The categories according to World Health Organization guidelines are listed in Table 3.

Table 3: Relationship of AE to Study Drug or Trial-Related Procedures

Rating	Classification	Definition
1	Probable	An AE that: 
• Occurs at a reasonable time interval after administration of the

		study drug;
		
 • Follows a known response pattern to the study drug and; • Cannot be reasonably explained by the known characteristics of the patient's clinical state or by other therapies
2	Possible	An AE that: 
 • Occurs at a reasonable time interval after administration of the study drug; • Follows a known response pattern to the study drug, but; • Could have been produced by the patient's clinical state or by other therapies
3	Unlikely	
 • An AE for which sufficient information exists to indicate that the etiology is unrelated to the study drug; • Another etiology is specified

If the AE is classified as unlikely, the PI should provide a likely cause, other illness, concomitant medication, or other.

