Faraday has conducted a phase 1 single ascending dose study in healthy volunteer subjects at intravenous doses of up to 10 mg/kg. No significant adverse events were detected, including biochemical measures of thyroid function. The anticipated therapeutic dose is likely in the range of 0.5 to 2.0 mg/kg based on nonclinical studies and human PK data.

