11.5.1 Adverse Events

The study specifically recruits STEMI patients; therefore the myocardial infarction (MI) itself will not be characterized as an AE. However, complications arising as a consequence of the MI, for example, an emergent or worsening heart failure, death, or arrhythmias will be specifically documented as adverse events in the CRFs.

A baseline sign and symptom is defined as an AE that starts after the patient has provided written informed consent and that resolves prior to the first dosing occasion, or an AE that starts prior to the first dosing occasion and does not increase in severity after dosing. A treatment-emergent AE (TEAE) is defined as an AE that occurs postdose or that is present predose and becomes more severe postdose.

All AEs will be listed. The TEAEs will be summarized by treatment, severity, and relationship to the study drug. The frequency (the number of TEAEs, the number of patients experiencing a TEAE, and the percentage of patients experiencing a TEAE) of TEAEs and serious TEAEs will be summarized by treatment, and by MedDRA system organ class and preferred term. The summary and frequency TEAE tables will be presented for all causalities and for those TEAEs considered related to the study drug (those that have a relationship of probable or possible). A subset of serious adverse events and adverse events which are cardiac related, including the development of heart failure, will also be presented as summary tables. For any AEs that change severity ratings the AE will be included only once under the maximum severity rating in the summaries. Any life-threatening, severe or serious AEs will be listed.

Onset times postdose are calculated from the start of study drug infusion.

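### Protocol Table 3 has no causality grade for a well-timed adverse event with no known response pattern and no established other cause, so the related-event tables cannot count it

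*Protocol*

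**What the plan says.** Protocol 13.2 makes grading compulsory: "The principal investigator (PI) will classify every AE according to its relationship to study drug or trial-related procedures". Protocol 13.1 lists relatedness among the attributes the investigator must assign. Table 3 offers three grades and no unassessable or other residual grade.

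- **Probable**: reasonable timing; "Follows a known response pattern to the study drug and"; and "Cannot be reasonably explained by the known characteristics of the patient's clinical state or by other therapies".
- **Possible**: reasonable timing; "Follows a known response pattern to the study drug, but"; and "Could have been produced by the patient's clinical state or by other therapies".
- **Unlikely**: "An AE for which sufficient information exists to indicate that the etiology is unrelated to the study drug", with another cause specified. A note under the table asks the investigator to name the likely cause.

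SAP 11.5.1 presents the TEAE tables twice: for all causalities, and for related events, defined as "those that have a relationship of probable or possible". Protocol 14.1.1 and 14.1.6 also summarise adverse events by relationship. SAP 11.1 does not impute missing values, so a blank rating would not be counted as related.

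On prior experience, Protocol 3.2 reports of Phase 1 that "No significant adverse events were detected, including biochemical measures of thyroid function". Protocol 3.3 says the drug has not yet been tested in AMI patients.

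**The concern.** Probable and Possible share two conditions, timing and a known pattern. They differ only on whether something else could explain the event. A reaction not seen before fails the shared pattern condition and so fails both grades. Unlikely is not a fallback, because it demands positive evidence of a different cause. An investigator facing a well-timed event with no established explanation must choose a grade, and none is correct.

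Two outcomes are possible. If the event is forced into Unlikely or left blank, it drops out of the related tables. If the investigator chooses Possible against the wording, grading may differ across as many as 20 centres. Neither is desirable in the first study in patients, where both documents make safety the primary focus. The protocol also does not list the known response patterns, so Table 3 gives sites no common reference for the condition that decides the grade.

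**Working it through.** The documents give no figure for this point, so the check is logical. Each Table 3 criterion is treated as true or false:

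- T: timing is reasonable.
- K: the event follows a known response pattern.
- X: another explanation could exist.
- U: the event is shown to be unrelated, with another cause named. U implies X.

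The grades are then:

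- Probable = T and K and not X
- Possible = T and K and X
- Unlikely = U

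T and K give 4 combinations. X and U give 3 (no alternative; alternative possible but not shown; other cause shown). That makes 4 × 3 = 12 coherent profiles.

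| Timing / pattern | No alternative | Alternative possible, not shown | Other cause shown |
|---|---|---|---|
| Reasonable / known | Probable | Possible | Possible and Unlikely |
| Reasonable / not known | none | none | Unlikely |
| Not reasonable / known | none | none | Unlikely |
| Not reasonable / not known | none | none | Unlikely |

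Results:

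1. Profiles with no grade: 0 + 2 + 2 + 2 = 6 of 12.
2. Profiles with two grades: 1 of 12.
3. Second row, the novel well-timed event: 2 of 3 profiles have no grade, the third is Unlikely, and none reaches Probable or Possible. Read literally, none can enter the related tables.

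These counts describe how the definitions fit together. They do not say how often each profile will occur, and the documents give no rate for novel reactions. As an assumption only, take a per-patient rate p of 1%, 2% or 5% among the 60 evaluable patients planned on active drug. The chance of at least one such event is 1 − (1 − p)^60:

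- p = 1%: 1 − 0.99^60 = 45%
- p = 2%: 1 − 0.98^60 = 70%
- p = 5%: 1 − 0.95^60 = 95%

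If 60 evaluable patients are reached, at least that many will have been dosed, so these are minimum values for the assumed rates.

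**The case against.** The best case against acting is that little depends on the related tables. Protocol 13.1 records every post-dose event whether or not it is attributed to the drug. SAP 11.5.1 lists all adverse events and tabulates TEAEs and serious TEAEs by arm for all causalities, with a cardiac subset. Protocol 13.4 defines and reports serious events without regard to relationship. In a randomised, double-blind trial, a new reaction shows as an imbalance between arms, and investigator attribution is not needed to see it. SAP 11.5.6 plans no inferential safety analysis, and no rule in the documents uses the related tables. All of this stands, and it limits the point to the summaries by relationship. It does not make those summaries correct.

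A reader might infer that no human response pattern is known, so the related tables would be empty. The documents do not support that. The Phase 1 statement is limited to significant events. Protocol 3.2 cites experience with oral iodide and intravenous use in thyrotoxic crisis, and reports gastro-intestinal inflammation in dogs. Protocol 6.2 excludes known iodide allergy and thyroid disease, and Protocol 12.2.2 measures thyroid function. The Investigators Brochure, which is not among the documents, may describe more. Events of recognised kinds can be graded related.

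It can also be said that investigators will use judgement. Protocol 13.3 expressly bases intensity on clinical judgement, whereas 13.2 sets fixed criteria for causality. Relying on judgement there means departing from the text. Protocol 13.2 attributes the categories to WHO guidelines, but that does not make the printed grades exhaustive.

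**Conclusion.** The point holds in a limited form. As printed, the three grades are neither exhaustive nor mutually exclusive: 6 of 12 coherent profiles have no grade and 1 has two. A well-timed event without a known pattern cannot be graded related, and unless another cause is established it cannot be graded at all. The effect falls on the related-TEAE tables and the other summaries by relationship.

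It would go too far to say that the trial would miss a new reaction, because the listings, the all-causality tables by arm and SAE reporting all keep it. To say that 0% of unexpected events could be graded related only restates the definition and does not measure the loss.

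The conclusion assumes that investigators apply Table 3 as written. How many events are affected cannot be estimated from the documents. The change is worth making because a stated rule misclassifies the kind of event a first study in patients should be able to flag, and a short edit repairs it.

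**What to change.** Amend Table 3 and the matching CRF text:

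- **Probable**: unchanged.
- **Possible**: delete the known-pattern criterion. Define the grade as a reasonable time interval with no other cause established, for events that do not meet Probable. This must include events whose other causes have been excluded. Wording that asks for another cause to be neither established nor excluded would leave out that strongest form of a new reaction.
- **Unlikely**: make it the residual grade, for events without a reasonable time interval or with another cause established. Apply the request to name a cause only where one is established.

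In the notation above, Possible becomes T and not U and not Probable, and Unlikely becomes not T or U. The 12 profiles then divide as follows:

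| Timing / pattern | No alternative | Alternative possible, not shown | Other cause shown |
|---|---|---|---|
| Reasonable / known | Probable | Possible | Unlikely |
| Reasonable / not known | Possible | Possible | Unlikely |
| Not reasonable / either | Unlikely | Unlikely | Unlikely |

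The last row stands for 6 profiles. The totals are Probable 1, Possible 3 and Unlikely 2 + 6 = 8, which sum to 12 with no gap and no overlap. Changing the Possible row alone would leave the 4 ungraded profiles with implausible timing still ungraded.

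Keep the SAP definition of related as Probable or Possible. The cost is a small protocol amendment and a CRF text change. The downside is that somewhat more events will be graded Possible, so the related tables become less specific. The all-causality comparison by arm is unaffected.
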